# **5.2.** Number of Subjects and Centers

A total of 4 subjects were enrolled in the Monotherapy Safety Run-in Phase. A total of 6-12 subjects are anticipated in the Combination Safety Run-in Phase. A total of up to 18 subjects will be enrolled in the Expansion Phase for a total of N=28-34 for the study. Study centers include University of Arizona ([name]), and additional study centers as needed to ensure timely accrual to the study.

# **5.3.** Treatment Assignment

This is an open-label study. In the Monotherapy Safety Run-in Phase, subjects received E6201 by IV infusion over a 2-hour period at a dose of 320 mg/m^2 twice weekly (Day 1, 4, 8, 11,15 and 18)

Confidential 32
December 31, 2019 Protocol Amendment 4

for 3 weeks of a 28-day cycle. In the Combination Safety Run-in and Expansion Phases, subjects will receive E6201 by IV infusion over a 2-hour period at a dose of 320 mg/m² twice weekly (Day 1, 4, 8, 11, 15and 18) of a 28-day cycle, plus dabrafenib at a dose of 150 mg orally twice daily.

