## 5. INVESTIGATIONAL PLAN

# 5.1. Overall Study Design

This is a Phase 1 study of E6201 for the treatment of CNS metastases in BRAF V600-mutated metastatic melanoma. A total of N = 28 - 34 subjects with melanoma metastasized to the CNS will be included.

Selected subjects will be: both males and females age  $\geq 18$  years; histologically confirmed melanoma with BRAF V600 mutation with CNS metastasis; archived tumor sample from the primary, recurrent or metastatic disease with documented BRAF mutation; no prior treatment with BRAF or MEK inhibitors for systemic disease; recovered from all acute toxicities ( $\geq$  Grade 1) due to prior immunotherapy; determined to have adequate renal and hepatic function, and no known history of significant cardiac disease.

Monotherapy Safety Run-in Phase: Following screening, a total of 4 subjects were enrolled. E6201 was administered by intravenous (IV) infusion over a 2-hour period at a dose of 320 mg/m^2 twice weekly (Days 1, 4, 8, 11, 15 and 18) for 3 weeks, repeated every 28 days (1 cycle), until progression of disease, observation of unacceptable adverse events, intercurrent illness or changes in the subject's condition that prevented further study participation.

Combination Safety-Run-in Phase: Following screening, a total of 6 - 12 subjects are anticipated to establish the recommended doses of E6201 plus dabrafenib. E6201 will be administered by IV infusion over a 2-hour period twice weekly (Days 1, 4, 8, 11, 15 and 18) repeated every 28 days plus dabrafenib orally twice daily (=1 cycle), according to the schedule below.

Dose Level	E6201 (IV)	Dabrafenib (PO)
1	320 mg/m² (MTD monotherapy)	150 mg BID (market dose)
-1ª	240 mg/m² (Dose Level -1)	150 mg BID
-2ª	240 mg/m² (Dose Level -1)	100 mg BID (Dose Level -1)
-3ª	160 mg/m² (Dose Level -2)	100 mg BID (Dose Level -1)
-4 a	160 mg/m² (Dose Level -2)	75 mg BID (Dose Level -2)
-5 a	160 mg/m² (Dose Level -2)	50 mg BID (Dose Level -3)

<sup>a If necessary based on DLT ( $\geq 1$  of 3 or  $\geq 2$  of 6 subjects experience DLT at the previous dose level)

Subjects who demonstrate clinical benefit (objective response or stable disease) will be allowed to continue therapy with E6201 plus dabrafenib until progression of disease, observation of unacceptable adverse events, intercurrent illness or changes in the subject's condition that prevents further study participation.

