Dose-limiting toxicity (DLT) is defined as any one of the following events:

- Grade 4 hematologic toxicity for > 1 day
- Grade 3 hematologic toxicity with complications (e.g., thrombocytopenia with bleeding)
- Failure of Grade 3 thrombocytopenia, absolute neutrophil count (ANC), hemoglobin to recover to Grade ≤ 1 within 4 weeks despite the use of platelet and red blood cell (RBC) transfusions and/or growth factors

Confidential 30
December 31, 2019 Protocol Amendment 4

• ≥ Grade 3 non-hematologic toxicity not due to disease progression (excluding Grade 3 nausea, vomiting or diarrhea that is adequately controlled with supportive care and resolves to ≤ Grade 2 within 48 hours, or Grade 3 electrolyte disturbances responsive to correction within 24 hours)

- ≥ Grade 3 liver function tests (LFTs) lasting > 72 hours
- Treatment interruption > 14 days due to toxicity
- Other important medical event

Subjects who require a dose reduction due to toxicity will be considered to have had a DLT.

If a DLT is experienced in  $\geq 2$  of 6 subjects in the Combination Safety Run-in Phase during Cycle 1, no further subjects will be enrolled at that dose level. Subjects who experience a DLT may continue treatment at the next lower dose level until disease progression or unacceptable toxicity. The MTD is defined as the doses of E6201 plus dabrafenib at which  $\leq 1$  of 6 subjects experiences a DLT.

E6201 dose reductions for suspected E6201-related toxicity will be 240 mg/m^2 twice weekly (Dose Level -1) and 160 mg/m^2 twice weekly (Dose Level -2), administered over the same schedule as above, Days 1, 4, 8, 11, 15 and 18, repeated every 28 days.

Dabrafenib dose reductions for suspected dabrafenib-related toxicity will be 100 mg (Dose Level -1), 75 mg (Dose Level -2) and 50 mg (Dose Level -3) orally twice daily, according to the U.S. Product Label.

A total of 6 subjects will be treated at the combined MTD doses for both drugs established in the Combination Safety Run-in Phase before beginning the Expansion Phase.

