Expansion Phase: Following screening, an additional cohort of up to N=18 subjects will be treated at the E6201 plus dabrafenib combined MTD. Subjects treated at the MTD in the Combination Safety Run-in Phase will count towards accrual in the Expansion Phase. E6201 will be administered by IV infusion over a 2-hour period at the MTD and schedule determined in the Combination Safety Run-in phase, repeated every 28 days (=1 cycle), and dabrafenib will be administered orally twice daily at the MTD determined in the Combined Safety Run-in phase. Both regimens will be subject to dose reductions for toxicity, as described. Subjects who demonstrate clinical benefit (objective response or stable disease) will be allowed to continue therapy with E6201 plus dabrafenib until progression of disease, observation of unacceptable adverse events, intercurrent illness or changes in the subject's condition that prevents further study participation.

During the study, a Safety Review Committee (SRC), consisting of the actively recruiting investigators, the Sponsor Medical Monitor and study staff will review data from the Monotherapy and Combination Safety Run-in Phases before beginning the Expansion Phase, and will review data from the Expansion Phase on an ongoing basis.

The statistical objective is the evaluation of the intracranial disease objective response (OR) rate, defined as complete response (CR) or partial response (PR), on treatment with E6201 plus dabrafenib. The sample size is based on a one-arm binomial design  $H_0 \le 0.05$  ( $\le 5\%$  response rate for historical control group) versus  $H_1 > 0.05$  (> 5% response rate for experimental group). An objective response (OR) rate of 25% or greater is deemed clinically important. A total of 3 or more

Confidential 31
December 31, 2019 Protocol Amendment 4

responses in a sample size of 18 subjects indicates the true OR rate is  $\geq$  25%, with power of = 80%, alpha = 0.05, and provides evidence of clinical utility to move forward.

CNS disease response will be assessed according to 2 methodologies: Response Evaluation Criteria in Solid Tumors (RECIST v. 1.1). and Response Assessment in Neuro-Oncology – Brain Metastases (RANO-BM). Clinical benefit is defined as best response of CR), (PR) or stable disease (SD).

Non-CNS systemic disease will be assessed according to RECIST v. 1.1.

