#### 8. STUDY DRUG MATERIALS AND MANAGEMENT

#### 8.1. E6201

#### 8.2. Study Drug Description

E6201 for Injection is a natural product analog and inhibitor of mitogen-activated protein kinase/extracellular-signal regulated kinase kinase-1 (MEK1). It is a sterile white lyophilized powder containing 60 mg of E6201 formulated in cyclodextrin to improve E6201 solubility in water. See Table 8 for a description of the drug product. The final study drug product will be administered at 320 mg/m² in a total volume of 250 mL intravenously over a 2-hour period twice weekly.

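### Section 5.3 fixes one dose pair for both combination phases while Section 5.1 assigns doses by dose level and MTD; after any de-escalation the two conflict

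*Combined protocol and SAP*

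**What the plan says.** Section 5.3 covers the Combination Safety Run-in and the Expansion Phase in one sentence: "In the Combination Safety Run-in and Expansion Phases, subjects will receive E6201 by IV infusion over a 2-hour period at a dose of 320" (the unit is mg/m² and the schedule is two infusions a week), and for the second drug "plus dabrafenib at a dose of 150 mg orally twice daily". It does not call this a starting dose, and it mentions neither dose levels nor the MTD.

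Section 5.1 handles the two phases differently.

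- **Combination Run-in.** E6201 is given "plus dabrafenib orally twice daily (=1 cycle), according to the schedule below". That schedule is a table of six levels, from Level 1 (320 mg/m² with 150 mg twice daily) down to Level -5.
- **Closing a level.** If 2 or more of 6 subjects have a DLT in Cycle 1, "no further subjects will be enrolled at that dose level".
- **MTD.** It is left open until the run-in is complete: "The MTD is defined as the doses of E6201 plus dabrafenib at which" at most 1 of 6 subjects has a DLT.
- **Expansion.** For E6201 the text is "E6201 will be administered by IV infusion over a 2-hour period at the MTD and schedule determined in the Combination Safety Run-in phase". For the oral drug it is "dabrafenib will be administered orally twice daily at the MTD determined in the Combined Safety Run-in phase".

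The synopsis (Section 1, Methodology) matches 5.1. Section 8.2 repeats the fixed figure ("The final study drug product will be administered at 320" mg/m²), and Table 8 lists 320 mg/m² as the unit dose. Section 8.6 refers only to the dose level that the protocol prescribes.

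**The concern.** Section 5.3 is where a site would look to find out what a newly enrolled subject receives. Read as written, it assigns the Level 1 pair to every new subject in both combination phases, whatever the run-in has shown. Section 5.1 makes the dose depend on the run-in.

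De-escalation is a planned outcome, since five lower levels are listed. The disagreement would therefore appear when DLTs have occurred and the dose for the next subject matters most. At stake is a safety-relevant assignment rule. If sites read it differently, there is also a risk that the Expansion cohort, which 5.1 places at a single combined MTD, would contain mixed doses. Both versions allow additional study centers, so more than one team may have to interpret the text.

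**Working it through.** The plan gives no figure on this point to reproduce. The check is a comparison of texts, followed by an illustration of how often the conflict would arise.

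**Step 1: compare each level in the 5.1 table with the 5.3 pair (320 mg/m² E6201, 150 mg dabrafenib twice daily).**

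| Level (5.1) | E6201, mg/m² | Dabrafenib, mg twice daily | E6201 ÷ 320 | Dabrafenib ÷ 150 | Same as 5.3? |
|---|---|---|---|---|---|
| 1 | 320 | 150 | 100% | 100% | Yes |
| -1 | 240 | 150 | 75% | 100% | No |
| -2 | 240 | 100 | 75% | 67% | No |
| -3 | 160 | 100 | 50% | 67% | No |
| -4 | 160 | 75 | 50% | 50% | No |
| -5 | 160 | 50 | 50% | 33% | No |

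Only Level 1 agrees. The first de-escalation separates the sections on E6201, and from Level -2 they differ on dabrafenib too.

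**Step 2: look for a text that says which section governs.**

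- Sections 5.5 and 5.5.1.2 repeat the closing rule, but their dose reductions are for a subject who has already had toxicity. They do not set the dose of a new subject after a cohort de-escalation.
- Section 8.6 points to the dose level prescribed by the protocol, which leads back to 5.1 and 5.3.
- Section 3.4.2 ties the same pair to the Combination Run-in and mentions dose reduction criteria. Section 5.3 has neither limit and names the Expansion Phase.
- No order of precedence between sections is stated.

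**Step 3: illustrate how often Level 1 would close.** Let p be the true Cycle 1 DLT probability per subject. The documents give no value, so 10%, 20% and 30% are assumptions. Two rules are worked because the body of 5.1 and the footnote to its dose table differ.

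Body text, 2 or more of 6: P = 1 − (1−p)^6 − 6p(1−p)^5

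- p = 0.10: 1 − 0.531 − 0.354 = 0.114
- p = 0.20: 1 − 0.262 − 0.393 = 0.345 (0.3446 before rounding, so 34%)
- p = 0.30: 1 − 0.118 − 0.303 = 0.580

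Footnote, read as 1 or more of the first 3, and otherwise 2 or more of 6: P = [1 − (1−p)³] + (1−p)³ × [3p²(1−p) + p³]

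- p = 0.10: 0.271 + 0.729 × 0.028 = 0.291
- p = 0.20: 0.488 + 0.512 × 0.104 = 0.541
- p = 0.30: 0.657 + 0.343 × 0.216 = 0.731

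| Assumed DLT rate | 10% | 20% | 30% |
|---|---|---|---|
| Level 1 closes, body text | 11% | 34% | 58% |
| Level 1 closes, footnote | 29% | 54% | 73% |

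**The case against.** The best defence is that 5.3 simply restates the starting dose, and that several other provisions stand between its wording and a wrongly dosed subject. Section 5.1 bars further enrolment at a closed level and requires six subjects at the MTD before Expansion. The Safety Review Committee, which includes the recruiting investigators and the Medical Monitor, reviews the run-in data before Expansion begins. Monthly safety calls review dose exposure and DLTs (Section 10.3.1.8). Section 8.6 leaves the dose level open.

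These safeguards do make misdosing less likely, and a reader should not infer that sites would in practice treat subjects at a closed level. They do not resolve the text. Section 5.3 does not describe a starting dose, and it names a phase whose dose 5.1 sets at the MTD.

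It is also fair to say that 8.2 and Table 8 are weak support. They describe the product and mention neither Expansion nor the MTD. Table 5 does use unit dose as the base for a 50% reduction, so the term has some operational use, but the contradiction rests on 5.3.

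A reader might also infer that the primary endpoint is defined at the combined MTD, so that the conflict alters the endpoint itself. The documents do not support this. Sections 10.4.1.1, 11.1 and 11.3.2.1 tie the endpoint to E6201 plus dabrafenib treatment without mention of the MTD, and Section 11.2 separates efficacy analyses by monotherapy and combination phases. Only the Expansion cohort's treatment is tied to the MTD, in 5.1 and the synopsis.

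**Conclusion.** The inconsistency is real but conditional. If Level 1 proves to be the MTD, 5.3 and 5.1 agree. If any de-escalation occurs, they prescribe different doses for new subjects: for E6201 at all five lower levels, and for dabrafenib at four of them. Section 5.3 would then assign a level at which 5.1 stops enrolment.

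The textual finding needs no assumption. The probabilities do: they rest on DLT rates that are not in the documents, on independent subjects with a common rate, and on the stated reading of the footnote. They measure how often the conflict would arise. They should not be read as the chance that anyone is misdosed, which cannot be calculated from the documents.

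The point should be acted on because it concerns a safety-relevant rule and is cheap to correct. It does not change the design, the sample size or the definition of the primary endpoint.

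**What to change.** Sections 5.3 and 5.1, with the synopsis, must be reconciled so that one dose assignment applies to new subjects in each phase, including after a de-escalation. The fixed 320 mg/m² in 8.2 and Table 8 must then be made consistent with the result. This review takes no view on which dose or rule is right; that is for the sponsor and the investigators to settle.

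The cost is a wording amendment centred on 5.3, with consequential edits to 8.2 and Table 8. No change to the sample size or the analysis is needed.

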# 5.4. Duration of Study

Accrual is expected to be 24 months, with the last subject followed for up to 6 months. The total study duration is expected to be 30 months. The anticipated accrual rate is 1-2 subjects per month.

# 5.5. Dose Adjustment Criteria

Subjects who experience a toxicity requiring dose reduction may continue at the next lower dose level until disease progression or unacceptable toxicity. Adverse events considered for dose reduction should not include the events assessed by the investigator as exclusively related to underlying disease or other medical condition or concomitant treatment.

# 5.5.1. Safety Criteria for Adjustment or Stopping Doses

# **5.5.1.1.** Toxicity Grading Criteria

Toxicity grading is based on NCI Common Terminology Criteria for Adverse Events Version 4.03 (CTCAE v4.03); http://evs.nci.nih.gov/ftp1/CTCAE/About.html.

# 5.5.1.2. Dose Modifications and Dose Reductions

Dose-limiting toxicity (DLT) is defined as any one of the following events:

- Grade 4 hematologic toxicity for > 1 day
- Grade 3 hematologic toxicity with complications (e.g., thrombocytopenia with bleeding)
- Failure of Grade 3 thrombocytopenia, absolute neutrophil count (ANC), hemoglobin to recover to Grade ≤ 1 within 4 weeks despite the use of platelet and red blood cell (RBC) transfusions and/or growth factors
- ≥ Grade 3 non-hematologic toxicity not due to disease progression (excluding Grade 3 nausea, vomiting or diarrhea that is adequately controlled with supportive care and resolves to ≤ Grade 2 within 48 hours, or Grade 3 electrolyte disturbances responsive to correction within 24 hours)
- $\geq$  Grade 3 liver function tests (LFTs) lasting > 72 hours
- Treatment interruption > 14 days due to toxicity
- Other important medical event

Subjects who require a dose reduction due to toxicity will be considered to have had a DLT.

No DLTs were experienced in the Monotherapy Safety Run-in Phase and no dose reductions were required for toxicity. If a DLT is experienced in  $\geq 2$  of 6 subjects in the Combination Safety Run-in Phase during Cycle 1, no further subjects will be enrolled at that dose level. Subjects who experience a DLT may continue treatment at the next lower dose level until disease progression or

Confidential 33
December 31, 2019 Protocol Amendment 4

unacceptable toxicity. The MTD is defined as the doses of E6201 plus dabrafenib at which  $\leq$  1 of 6 subjects experiences a DLT.

Subjects who experience E6201- and/or dabrafenib-related toxicity requiring a dose reduction may continue treatment at the next lower dose level for either drug until disease progression or unacceptable toxicity. Adverse events considered for dose reduction should not include the events assessed by the investigator as exclusively related to underlying disease or other medical condition or concomitant treatment. If treatment must be delayed for reasons other than toxicity, contact the Medical Monitor to discuss the reasons for delay and plans for resuming study therapy.

The E6201 dose modification guidelines are outlined in Table 4. Provisions are not made for dose levels below 160 mg/m² twice weekly. If 160 mg/m² twice weekly is determined to be unsuitable based on toxicity as defined above, the subject will be permanently discontinued from E6201 treatment.

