Blood for hematology and serum chemistry determinations will be collected within 28 days of Cycle 1 Day 1 and on Day 1 of each cycle and at the End of Treatment Visit.

ECGs will be taken within 28 days prior to Cycle 1 Day 1, pre-infusion and 5 minutes following the end of the E6201 2-hour infusion, on Day 1 of every cycle thereafter, and at the End-of-Study visit.

CNS and non-CNS systemic disease assessments will be based on magnetic resonance image (MRI) or computed tomography (CT) if unable to perform MRI for intracranial disease. Assessments will be obtained at Week 8 and every 8 weeks thereafter until documented progression of disease (PD). Subjects who demonstrate clinical benefit will be allowed to continue therapy until progression of disease, observation of unacceptable adverse events, intercurrent illness or changes in the subject's condition that prevents further study participation.

Safety will be assessed through the monitoring of adverse events (AEs), clinical laboratory parameters (hematology and serum chemistry), vital sign measurements, ECGs and physical examinations. Adverse events will be classified according to the Medical Dictionary for Regulatory Affairs (MedDRA) and graded according to the National Cancer Institute Common Terminology Criteria for Adverse Events (NCI CTCAE) version 4.03.

Efficacy assessments will be determined on the basis of MRI and/or CT scans with best treatment response at any protocol-specified time point for intracranial disease, duration of response, duration of stable disease, and time to CNS metastasis disease progression based on RECIST v.1.1 and RANO-BM. Response rates also will be determined for non-CNS systemic disease. Progression-free survival (PFS) and overall survival (OS) will be evaluated.

A correlation will be made between *BRAF* mutational status (e.g., type, heterozygosity or homozygosity) in archival tissue with clinical outcome.

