#### 9.1. Screening Procedures

The following evaluations are to be performed within 28 days of study treatment to determine subject eligibility:

- Administration of informed consent
- Medical history, physical examination and vital signs
- ECOG Performance Status
- Height and weight
- The following laboratory tests:
  - Hematology
  - Serum Chemistry
- Beta HCG pregnancy test for WCBP
- 12-lead ECG
- Review of concomitant medications
- Baseline CT or MRI of systemic and intracranial disease

## 9.2. Requirements During Treatment Cycle 1

#### 9.2.1. Cycle 1, Day 1

- Abbreviated physical examination
- Vital signs
- ECOG Performance Status
- Weight
- The following lab tests
  - Hematology, if not performed within previous 24 hours
  - Serum chemistry, if not performed within previous 24 hours
- E6201 study drug administration (Day 1 and Day 4)
- Begin twice daily dabrafenib treatment and provide Dabrafenib Patient Medication Diary to subject (applicable to Combination Phases of study only)
- 12-lead ECG, pre-dose, at 5 minutes after the infusion ends ( $\pm$  5 minutes)
- Review of concomitant medications

Confidential 46
December 31, 2019 Protocol Amendment 4

- Assessment of adverse events
- Assessment for survival

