#### 9.2.2. Cycle 1, Day 8 ( $\pm$ 1 day)

- Vital signs
- ECOG Performance Status
- E6201 study drug administration (Day 8 and Day 11)
- Continue dabrafenib twice daily treatment
- Review Dabrafenib Patient Medication Diary with subject (applicable to Combination Phases of study only)
- Review of concomitant medications
- Assessment of adverse events
- Assessment for survival

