#### 9.2.3. Cycle 1, Day 15 ( $\pm$ 1 day)

- Vital signs
- ECOG Performance Status
- E6201 study drug administration (Day 15 and Day 18)
- Continue dabrafenib twice daily treatment
- Review Dabrafenib Patient Medication Diary with subject (applicable to Combination Phases of study only)
- Review of concomitant medications
- Assessment of adverse events
- Assessment for survival

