## 9.3. Requirements During Treatment Cycles After Cycle 1 (Cycle 2 and beyond) [± 3 days]

- Abbreviated physical examination (Day 1 only)
- Vital signs
- ECOG Performance Status
- Weight (Day 1)
- The following lab tests:
  - Hematology, if not performed within previous 24 hours

Confidential 47
December 31, 2019 Protocol Amendment 4

- Serum chemistry, if not performed within previous 24 hours
- E6201 study drug administration (Days 1, 4, 8, 11, 15 and 18)
- Continue dabrafenib twice daily treatment
- Review Dabrafenib Patient Medication Diary with subject (applicable to Combination Phases of study only)
- 12-lead ECG pre-dose, at 5 minutes after the infusion ends ( $\pm$  5 minutes)
- Review of concomitant medications
- Assessment of adverse events
- Assessment for survival
- CT or MRI of systemic and intracranial disease for re-staging (Day 28 of even numbered cycles, ± 7 days)

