## APPENDIX D. SCHEDULE OF STUDY PROCEDURES

Study Activity	Screening a	Treatment Cycle 1		Treatment Cycles after Cycle 1		Progression or Relapse	End of Treatment l	Long-Term Follow-Up n	
		Day 1	Day 8 i	Day 15 i	Day 1	End of Cycle 2 j,k			
Signed ICD	X								
Medical History	X								
Physical Examination	X	X			X h			X	
Vital Signs	X	X	X	X	X			X	
ECOG Perform. Status	X	X	X	X	X			X	
Height	X								
Weight	X	X			X			X	
Hematology b	X	X			X			X	
Serum Chemistry c	X	X			X			X	
Beta-hCG for WCBP	X								
12-lead ECG	X	X d			X d			X	
Concomitant Medications	X	Continuous							
AE Assessment		Continuous							
Disease Assessment e	X					X	X		
E6201 Administration f		X (+D4)	X (+D11)	X (+D18)	X (D 1, 4, 8, 11, 15, 18)				
Dabrafenib Dosing g,m		X	X	X	X			X m	
Assessment of Survival		X			X	X	X	X	X

- a Screening to be performed within 28 days of Cycle 1, Day 1
- b Hematology parameters collected at Screening, Cycle 1 Day 1 (only if not performed in the previous 24 hours), Day 1 of each subsequent cycle (within 3 days of Day 1 of each subsequent cycle) and End of Treatment. See Table 9 for tests to be conducted at each time point.
- c Serum chemistry collected at Screening, Cycle 1 Day 1 (only if not performed within the previous 24 hours), Day 1 of each subsequent cycle (within 3 days of Day 1 of each subsequent cycle) and End of Treatment. See Table 9 for tests to be conducted at each time point.
- d ECGs performed pre-dose and at the end of the E6201 2-hour infusion (± 5 minutes)
- e Disease Assessment may include CT, MRI, and/or physical exam
- f E6201 IV twice weekly Day 1,4, 8, 11, 15 and 18 of each 28-day cycle
- g Dabrafenib dose orally twice daily, continuously. Provide Dabrafenib Patient Medication Diary.
- h Abbreviated physical exam
- i Day 8, 15 ( $\pm 1$  day)
- j Day 28 (±7 days)
- k Perform at the end of every even numbered cycle thereafter
-  End of Treatment visit should be within 28 days from last dose of study medication (±5 days)
- m Review Dabrafenib Patient Medication Diary (each clinic visit + End of Treatment)
- n Long-term follow-up for 6 months consists of clinic visits or telephone calls every 3 months to assess survival status

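### Cycle 1 schedules no blood tests between Day 1 and the start of Cycle 2, so infusions 2 to 6 are given with no new scheduled laboratory value and asymptomatic laboratory toxicity can go unseen

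*Combined protocol and SAP*

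**What the plan says.** Section 5.1 sets the laboratory schedule: "Blood for hematology and serum chemistry determinations will be collected within 28 days of Cycle 1 Day 1 and on Day 1 of each cycle", plus the End of Treatment visit. Section 9.2.1 gives Cycle 1 Day 1 a panel ("Hematology, if not performed within previous 24 hours", and likewise chemistry), so infusion 1 is covered.

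The Day 8 and Day 15 visit lists (Sections 9.2.2 and 9.2.3) cover the infusions on Days 8, 11, 15 and 18. They include vital signs, performance status and adverse event assessment, but no blood tests. Appendix D agrees: the hematology and chemistry rows are blank for Days 8 and 15, and footnote b reads "Hematology parameters collected at Screening, Cycle 1 Day 1 (only if not performed in the previous 24 hours), Day 1 of each subsequent cycle". Footnote c says the same for chemistry.

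Three sets of rules depend on laboratory values in this window.

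- **DLT definition (Section 5.5.1.2).** It includes "Grade 4 hematologic toxicity for > 1 day" and liver tests of Grade 3 or worse for more than 72 hours. Grade 3 non-hematologic toxicity also counts, apart from exceptions such as "Grade 3 electrolyte disturbances responsive to correction within 24 hours". Any dose reduction for toxicity counts as a DLT.
- **Table 4.** E6201 is interrupted for related toxicity of Grade 2 or worse. The dose is reduced at a first Grade 3 or a second Grade 2.
- **Section 5.5.1.3.** Treatment resumes once the toxicity is Grade 1 or lower.

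**The concern.** These rules act only on abnormalities that someone has measured. A cytopenia or liver enzyme rise without symptoms is found by a blood test, and none is scheduled while infusions 2 to 6 are given. A subject with such an abnormality would be dosed again when Table 4 calls for a hold.

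The same gap affects dose finding. Missed events can only lower the DLT count. Dose Level 1 is the starting pair and every other level is lower, so the possible error is to keep the starting pair, or to stop de-escalating, too soon. That dose then goes into the Expansion Phase, where the primary response rate is measured.

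Laboratory toxicity is plausible. In the solid-tumor study (Section 3.1.4), related hypokalemia occurred in 3 of 25 (12.0%) and 4 of 30 (13.3%) subjects, and Grade 3/4 hyperbilirubinemia, regardless of cause, in 2 of 25. The one E6201-related event in this trial's monotherapy run-in was Grade 2 thrombocytopenia, in a subject with that history (Section 3.4.1).

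**Working it through.** The plan states no figure on this point to reproduce. The first step is a count from the schedule. The rest is illustration.

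**1. Gap between scheduled draws.** The infusion days are 1, 4, 8, 11, 15 and 18. The last scheduled draw before infusions 2 to 6 is on Day 1, so these infusions come 3, 7, 10, 14 and 17 days after it. Cycle 2 Day 1 is Day 29 ± 3, that is Day 26 to 32, or 8 to 14 days after the sixth infusion. Five of six infusions have no same-day panel. With panels on Days 8 and 15 this falls to three of six, and the longest time from a panel to an infusion falls from 17 days to 3.

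**2. Coverage.** Assume onset is uniform over the 28 days from Day 1 to Day 29, with no symptoms and no unscheduled test. For an abnormality lasting d days (d ≤ 7), the share seen at a scheduled draw is:

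- as planned (Day 29 only): c = d/28
- with Days 8 and 15 added: c = 3d/28

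Counting whole onset days from Day 2 to Day 28 instead gives 4% and 22% as planned for 2- and 7-day events, and 19% and 74% with the added panels. The picture is the same. Longer events fare better: at 14 days, Cycle 2 Day 1 alone sees 14/28 = 50%.

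**3. Effect on accepting the dose.** Section 5.5.1.2 accepts a dose with at most 1 DLT in 6 subjects. Take a true DLT rate of 0.33 and assume that 25% of DLTs are laboratory-only. The observed rate is

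p = 0.33 × [1 − 0.25 × (1 − c)]

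and the chance of acceptance is

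A = (1 − p)^6 + 6p(1 − p)^5.

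If every DLT is seen, p = 0.33 and A = 0.36.

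| Duration | c as planned | p | A | c with Days 8, 15 | p | A |
|---|---|---|---|---|---|---|
| 2 days | 7.1% | 0.253 | 0.53 | 21.4% | 0.265 | 0.50 |
| 3 days | 10.7% | 0.256 | 0.52 | 32.1% | 0.274 | 0.48 |
| 7 days | 25.0% | 0.268 | 0.49 | 75.0% | 0.309 | 0.40 |

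With a 10% laboratory share, A moves only from 0.42 to 0.41 (2 days) and from 0.41 to 0.37 (7 days).

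**The case against.** Much of the case on the other side stands.

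- **Timing.** A reader might infer that the timed DLT criteria cannot be applied at all. The documents do not support that. Section 10.3.1.7 follows adverse events to resolution or baseline, Table 4 holds E6201 until recovery, and Section 5.5.1.3 allows resumption only at Grade 1 or lower. Once an abnormal value is found, these rules already imply retesting. The 24-hour electrolyte limit is most naturally read as running from correction, which follows detection. A related Grade 3 value usually becomes a DLT through the dose-reduction rule, however long it lasts. The weak point is finding the first value.
- **Size.** A reader might also infer that the maximum tolerated dose would be badly wrong. If half of DLTs were laboratory-only and all were missed, acceptance at a true 33% rate would be 0.74. That is not a credible upper value: the Cycle 2 panel, the adverse event checks on Days 8 and 15, and unscheduled tests (which are not forbidden) will catch some events. The DLT types named in the solid-tumor study were QTc prolongation and confusion, and the four monotherapy subjects had no DLT. Reading the dose-table footnote as the acceptance rule (none of 3, then at most 1 of the next 3) moves acceptance from 0.36 to 0.22 when all events are seen, more than the added panels do. That is a separate matter.
- **Other safeguards.** The Safety Review Committee and the monthly safety review look at laboratory abnormalities, but only those collected. Neither adds a draw. The C1D28 evaluation named in Section 6.3.2 has no stated content, and it falls after the last infusion.

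**Conclusion.** The gap is real. Sections 5.1 and 9.2.1 to 9.2.3 and Appendix D agree that nothing is drawn between Cycle 1 Day 1 and Cycle 2 Day 1, so the blank cells are not an extraction fault. Asymptomatic laboratory toxicity that resolves before Cycle 2 can go unseen while five infusions are given, and the only possible bias in the DLT count is downward.

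This should be fixed, and the reason is patient safety. The dose-selection figures rest on an assumed laboratory share, uniform onset and no incidental detection. They show a modest effect for short events and a larger one for week-long events. They do not show that the selected dose would be wrong, and nothing here invalidates the analysis of the primary response rate.

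**What to change.** Add the Table 9 hematology and chemistry panel before infusion on Cycle 1 Days 8 and 15. Change Sections 9.2.2 and 9.2.3, the two laboratory rows and footnotes b and c of Appendix D, and the matching sentence in Section 5.1 and the synopsis.

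Two clarifications are optional: a sentence requiring repeat tests after a laboratory value of Grade 3 or worse, and a definition of the C1D28 evaluation, which could be the pre-Cycle 2 panel.

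The direct cost is two routine panels per subject at visits already attended. There is also an indirect cost: some brief, asymptomatic abnormalities will newly trigger interruptions, reductions or DLTs, and may prompt de-escalation. Very short events, and the stretch from Day 15 to the end of the cycle, remain only partly covered.
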